10.4 Expedited Reporting Requirements for IND/IDE Agents

Phase 1 and Early Phase 2 Studies: Expedited Reporting Requirements for Adverse Events that Occur on Studies under an IND/IDE within 30 Days of the Last Administration of the Investigational Agent/Intervention 1, 2

[figure not shown]
| FDA REPORTING REQUIREMENTS FOR SERIOUS ADVERSE EVENTS (21 CFR Part 312) NOTE: Investigators MUST immediately report to the sponsor ANY Serious Adverse Events, whether or not they are considered related to the investigational agent(s)/intervention (21 CFR 312.64) An adverse event is considered serious if it results in ANY of the following outcomes: Death A life-threatening adverse event An adverse event that results in inpatient hospitalization or prolongation of existing hospitalization for ≥ 24 hours A persistent or significant incapacity or substantial disruption of the ability to conduct normal life functions A congenital anomaly/birth defect. Important Medical Events (IME) that may not result in death, be life threatening, or require hospitalization may be considered serious when, based upon medical judgment, they may jeopardize the patient or subject and may require medical or surgical intervention to prevent one of the outcomes listed in this definition. (FDA, 21 CFR 312.32; ICH E2A and ICH E6). | | | | | |
|---|--------------------------------|----------------------------|--|--|--|
| ALL SERIOUS adverse events that meet the above criteria MUST be immediately reported to the sponsor within the timeframes detailed in the table below. | | | | | |
| Hospitalization | Grade 1 and Grade 2 Timeframes | Grade 3-5 Timeframes | | | |
| Resulting in Hospitalization ≥ 24 hrs | 7 Calendar Days | 24-Hour 3 Calendar Days | | | |
| Not resulting in Hospitalization ≥ 24 hrs | Not required | | | | |
| NOTE: Protocol specific exceptions to expedited reporting of serious adverse events are found in Section 10.41 of the protocol. Expedited AE reporting timelines are defined as: "24-Hour; 3 Calendar Days" - The AE must initially be reported within 24 hours of learning of the AE, followed by a complete expedited report within 3 calendar days of the initial 24-hour report. "7 Calendar Days" - A complete expedited report on the AE must be submitted within 7 calendar days of learning of the AE. | | | | | |
| ¹Serious adverse events that occur more than 30 days after the last administration of investigational agent/intervention and have an attribution of possible, probable, or definite require reporting as follows: Expedited 24-hour notification followed by complete report within 3 calendar days for: All Grade 3, 4, and Grade 5 AEs Expedited 7 calendar day reports for: Grade 2 AEs resulting in hospitalization or prolongation of hospitalization ² For studies using PET or SPECT IND agents, the AE reporting period is limited to 10 radioactive half-lives, rounded UP to the nearest whole day, after the agent/intervention was last administered. Footnote "1" above applies after this reporting period. | | | | | |
| | Effective Date: May 5, 2011 | | | | |

Additional instructions:

- 1. Contact Ascenta and Celgene (see contact information below).
- 2. Use paper Adverse Event Expedited Report Single Agent or Multiple Agents report available in forms packet. Submit to:

Ascenta: Senior Manager

Safety & Pharmacovigilence Ascenta Therapeutics Inc. [name]

Celgene: Celgene Corporation Global Drug Safety and Risk Management Connell Corporate Park [name]

Mayo Clinic Cancer Center (MCCC) Institutions: Provide copies, along with the UPIRTSO cover sheet, by fax (to the MCCC Regulatory Affairs Unit (RAU) Risk Information Specialist who will determine and complete IRB reporting. The RAU will submit to the MCCC SAE Coordinator and the MCCC IND Coordinator to determine if FDA submission is needed.

| EVENT TYPE | REPORTING PROCEDURE | | |
|---|---|--|--|
| Other Grade 4 or 5 Events and/or Any Hospitalizations During Treatment Not Otherwise Warranting an Expedited Report | Complete a Notification Form: Grade 4 or 5 Non-AER Reportable Events/Hospitalization Form electronically via the MCCC Remote Data Entry System or paper form within 5 working days of the date the clinical research associate (CRA) is aware of the event(s) necessitating the form. If an expedited written report has been submitted, this form does not need to be submitted. | | |

10.41 Special Situations for Expedited Reporting and Submission of Notification Forms

Exceptions to Expedited Reporting and Submission of Notifcation Forms: EXPECTED Serious Adverse Events

An expedited report or notification form may not be required for specific Grade 1, 2 and 3 Serious Adverse Events where the AE is **EXPECTED**. Any protocol specific reporting procedures MUST BE SPECIFIED BELOW and will supercede the standard Expedited Adverse Event Reporting and Notification Form Requirements (Note: These adverse

| System Organ Class (SOC) | Adverse event/ Symptoms | CTCAE Grade at which the event will not be expeditedly reported ¹ . |
|--------------------------------------|----------------------------|--|
| Blood and lymphatic system disorders | Anemia | ≤4 |
| Investigations | White blood cell decreased | ≤ 4 |
| | Lymphocyte count decreased | ≤ 4 |
| | Neutrophil count decreased | ≤ 4 |
| | Platelet count decreased | < 4 |

events must still be reported through the routine reporting mechanisms [i.e. Nadir/adverse events form]; see footnote 1):

¹ These exceptions only apply if the adverse event does not result in hospitalization. If the adverse event results in hospitalization, then the standard expedited adverse events reporting requirments must be followed.

Specific protocol exceptions to expedited reporting should be reported expeditiously by investigators **ONLY** if they exceed the expected grade of the event.

10.5 Other Required Reporting

10.51 Persistent or Significant Disabilities/Incapacities

Any AE that results in persistent or significant incapacity or substantial disruption of the ability to conduct normal life functions (formerly referred to as disabilities), congenital abnormities or birth defects, must be reported immediately if they occur at any time following treatment with an agent under an IND/IDE since they are considered to be a serious AE and must be reported to the sponsor as specified in 21 CFR 312.64(b).

10.52 Death

Any death occurring within 30 days of the last dose, regardless of attribution to an agent/intervention under an IND/IDE requires expedited reporting within 24-hours.

Any death occurring greater than 30 days with an attribution of possible, probable, or definite to an agent/intervention under an IND/IDE requires expedited reporting within 24-hours.

Reportable categories of Death

- Death attributable to a CTCAE term.
- Death Neonatal: A disorder characterized by cessation of life during the first 28 days of life.
- Death NOS: A cessation of life that cannot be attributed to a CTCAE term associated with Grade 5.

- Sudden death NOS: A sudden (defined as instant or within one hour of the onset of symptoms) or an unobserved cessation of life that cannot be attributed to a CTCAE term associated with Grade 5.
- Death due to progressive disease should be reported as Grade 5 "Neoplasms benign, malignant and unspecified (incl cysts and polyps) – Other (Progressive Disease)" under the system organ class (SOC) of the same name. Evidence that the death was a manifestation of underlying disease (e.g., radiological changes suggesting tumor growth or progression: clinical deterioration associated with a disease process) should be submitted.
- 10.53 Secondary Malignancy
 - A *secondary malignancy* is a cancer caused by treatment for a previous malignancy (e.g., treatment with investigational agent/intervention, radiation or chemotherapy). A secondary malignancy is not considered a metastasis of the initial neoplasm.
 - All secondary malignancies that occur following treatment with an agent under an IND/IDE be reported. Three options are available to describe the event:
 - Leukemia secondary to oncology chemotherapy (e.g., Acute Myeloctyic Leukemia [AML])
 - Myelodysplastic syndrome (MDS)
 - Treatment-related secondary malignancy
 - Any malignancy possibly related to cancer treatment (including AML/MDS) should also be reported via the routine reporting mechanisms outlined in each protocol.
- 10.54 Second Malignancy
 - A second malignancy is one unrelated to the treatment of a prior malignancy (and is NOT a metastasis from the initial malignancy). Second malignancies require ONLY routine reporting.
- 10.55 Pregnancies

Pregnancies occurring while the subject is on study drug or within 4 weeks after the subject's last dose of study drug are considered immediately reportable events. If the subject is on study drug the study drug is to be discontinued immediately and the subject is to be instructed to return any unused portion of the study drug to the Investigator. The pregnancy must be reported to the Safety Monitor within 24 hours of the Investigator's knowledge of the pregnancy by phone and facsimile using the SAE Form.

Protocol Version Date: November 25, 2014

The Investigator will follow the subject until completion of the pregnancy, and must notify the Safety Monitor of the outcome within 5 days or as specified below. The Investigator will provide this information as a follow-up to the initial SAE.

If the outcome of the pregnancy meets the criteria for immediate classification as a SAE (i.e., spontaneous abortion [any congenital anomaly detected in an aborted fetus is to be documented], stillbirth, neonatal death, or congenital anomaly), the Investigator should follow the procedures for reporting SAEs (i.e., report the event to the Safety Monitor by telephone and facsimile within 24 hours of the Investigator's knowledge of the event).

All neonatal deaths that occur within 30 days of birth should be reported, without regard to causality, as SAEs. In addition, any infant death after 30 days that the Investigator suspects is related to the *in utero* exposure to the study drug should also be reported.

In the case of a live "normal" birth, the Safety Monitor should be advised as soon as the information is available.

10.6 **Required Routine Reporting**

Adverse events to be graded at each evaluation and pretreatment symptoms/conditions to be evaluated at baseline per the CTCAE v4.0 grading unless otherwise stated in the table below:

| System Organ Class (SOC) | Adverse event/Symptoms | Baseline | Each evaluation |
|--------------------------------------|---------------------------|----------|--------------------|
| Investigations | Platelet count decreased* | X | Х |
| Blood and lymphatic system disorders | Anemia* | X | Х |
| Gastrointestinal disorders | Constipation | Х | Х |
| | Ileus | | Х |

* Grading will be performed by the study statisticians at the time of analysis based on the CLL toxicity grading scale for blood counts in Appendix V. Anemia grade per CTCAE will also be recorded for reporting purposes.

- 10.61 Submit via appropriate MCCC Case Report Forms (i.e., paper or electronic, as applicable) the following AEs experienced by a patient and not specified in Section 10.6:
 - 10.611 Grade 2 AEs deemed *possibly*, *probably*, *or definitely* related to the study treatment or procedure.
 - 10.612 Grade 3 and 4 AEs regardless of attribution to the study treatment or procedure.
 - 10.613 Grade 5 AEs (Deaths)

Protocol Version Date: November 25, 2014

- 10.6131 Any death within 30 days of the patient's last study treatment or procedure regardless of attribution to the study treatment or procedure.
- 10.6132 Any death more than 30 days after the patient's last study treatment or procedure that is felt to be at least possibly treatment related must also be submitted as a Grade 5 AE, with a CTCAE type and attribution assigned.
- 10.62 Refer to the instructions in the Forms Packet (or electronic data entry screens, as applicable) regarding the submission of late occurring AEs following completion of the Active Monitoring Phase (i.e., compliance with Test Schedule in Section 4.0).

11.0 Treatment Evaluation

Note: Formal response evaluation should occur every 2 cycles during treatment, with the first response evaluation occurring at the end of cycle 2. Formal response evaluation should occur every cycle during observation. Objective status should be classified as PD vs. Not PD on cycles when a formal response evaluation does not occur.

11.1 Schedule of evaluations: For the purposes of this study, patients should be reevaluated for progression every 28 days during therapy with lenalidomide and AT-101. Formal response evaluation will occur every 2 cycles, with the first formal response evaluation occurring at the end of cycle 2. However, patients will be evaluated prior to each cycle of therapy to identify individuals who have experienced disease progression. Prior to the first formal response evaluation, baseline on study measurements will be used to determine disease progression (e.g. not cycle by cycle comparisons). Once patients undergo formal response evaluation, the nadir value at either baseline or time of response evaluation will be used for evaluating future disease progression. In addition to a baseline scan, confirmatory scans should also be obtained as needed to document objective response at sites of non-palpable lymphadenopathy or organomegaly as indicated in Section 4 or as needed clinically.

NOTE: Information from CT scans is not considered in the standard classification of response.

11.2 Definitions

The NCI Working Group criteria⁵⁹ will be used to assess response to therapy.

- 11.21 COMPLETE RESPONSE (CR) requires all of the following for a period of at least 2 months. The first formal response evaluation for CR should occur no sooner than the end of cycle 2.
 - 11.211 Absence of lymphadenopathy (e.g. lymph nodes >1.5 cm) by physical examination.
 - 11.212 No hepatomegaly or splenomegaly by physical examination.

- 11.213 Absence of constitutional symptoms.
- 11.214 CBC demonstrating:
 - Neutrophils >1500/ul.
 - Platelets >100,000/ul (untransfused).
 - Hemoglobin >11.0 gm/dl (untransfused).
 - Peripheral blood lymphocytes <4000/uL.

Note: Patients who fulfill all criteria for a CR but who have a persistent anemia, thrombocytopenia, or neutropenia related to drug toxicity rather than residual CLL will be classified as **CR with incomplete marrow recovery (CRi)** according to the international criteria⁵⁹.

11.215 Bone marrow aspirate and biopsy should be performed within two month after documentation of clinical and laboratory evidence of a complete response to document that a complete response (CR) has been achieved. The marrow sample should ideally be at least normocellular with <30% of nucleated cells being lymphocytes. Samples are to be analyzed by a pathologist and the presence or absence of nodules noted. Repeat bone marrow aspirate and biopsy are not necessary to document sustained CR.

In a subset of patients who are otherwise in a complete response, bone marrow nodules can be identified histologically. In such cases, special stains will be performed to determine whether such nodules represent "regenerative nodules" or residual "clonal nodules". The presence of regenerative nodules is consistent with CR while the presence of residual clonal nodules will be classified as an **nPR (nodular PR)** which is a sub-classification of PR.

Note: In a patient who achieves clinical and laboratory evidence of a complete response, the objective status should be recorded as a CCR on the cycle where the formal response evaluation occurred until a bone marrow biopsy and aspirate have been performed. At that time, the objective status should be amended to classify the patient as a CR, CRi, or nPR on the cycle where the formal response evaluation occurred.

- 11.216 Patients who have clinical and laboratory evidence of CR but who have not yet had a bone marrow biopsy to distinguish between CR and nPR will be classified as having a **Complete Clinical Response (CCR)** until the marrow biopsy is obtained.
- 11.217 In some settings MRD assays may be considered as a surrogate of response as discussed in section 11.3. No other laboratory assays (e.g., quantitative immunoglobulins) will be used currently as an index for response but will be recorded for clinical correlations.
- 11.218 For patients whose only measurable disease at the time of enrollment is on CT scan (i.e. SLL with no palpable nodes), a CT scan is required before classifying patients a CR.

Protocol Version Date: November 25, 2014

- 11.22 PARTIAL RESPONSE (PR) requires the patient exhibits at least two of the features in Sections 11.221, 11.222, and 11.223 below (if abnormal prior to therapy) as well as one or more of the remaining features (Sections 11.224, 11.225, 11.226) for at least 2 months. In addition to the parameters listed below, the presence or absence of constitutional symptoms will be recorded. The first formal response evaluation for PR should occur no sooner than the end of cycle 2.
 - $11.221 \ge 50\%$ decrease in peripheral blood lymphocyte count from the pretreatment baseline value.
 - $11.222 \ge 50\%$ reduction in the sum of the products of the maximal perpendicular diameters of the largest measured node or nodal masses in the right and left cervical, axillary, and inguinal lymph node regions on physical examination.
 - $11.223 \ge 50\%$ reduction in size of liver and/or spleen as measured by physical exam noting the maximal distance below the respective costal margins of palpable hepatosplenomegaly during rest.
 - 11.224 Neutrophils >1500/ul or 50% improvement over baseline.
 - 11.225 Platelets >100,000/ul or 50% increase over baseline.
 - 11.226 Hemoglobin >11.0 gm/dl or 50% increase over baseline without transfusions.
 - 11.227 For patients whose only measurable disease at the time of enrollment is on CT scan (i.e. SLL with no palpable nodes), a CT scan demonstrating > 50% reduction of target nodes enlarged at baseline is required before classifying patients a PR.
 - 11.228 For patients whose only measurable disease at the time of enrollment is on CT scan (i.e. SLL with no palpable nodes), a CT scan is required before classifying patients PR.
- 11.23 PROGRESSION (PD): Patients will receive protocol therapy unless they have evidence of disease progression according to the NCI criteria³ as evidenced by:
 - 11.231 ≥ 50% increase in the sum of the products of at least 2 lymph nodes on 2 consecutive determinations 2 weeks apart (at least one node must be ≥2 cm) or the appearance of new palpable lymph nodes >1.5 cm not due to a tumor flare. Enlargements or the appearance of new nodes due to a tumor flare do NOT qualify as progression.
 - $11.232 \ge 50\%$ increase in the size of the liver and/or spleen as determined by measurement below the respective costal margin on 2 consecutive determinations 2 weeks apart and with a minimum of $a \ge 2$ cm increase in size from baseline; or appearance of hepatomegaly or splenomegaly which was not previously present at baseline and not due to a tumor flare.

Protocol Version Date: November 25, 2014

- 11.233 Transformation to a more aggressive histology (e.g. Richter's transformation).
- $11.234 \ge 50\%$ increase in the absolute number of circulating lymphocytes NOT due to infection or tumor flare (taking as reference for progressive disease the smallest absolute lymphocyte count recorded since the treatment started). The absolute lymphocyte count must be at least $5000/\text{mm}^3$ to qualify as disease progression.
- 11.235 In the absence of progression as defined by 1, 2, 3, or 4 above, the presence of $a \ge 2$ g/dl decrease in HGB, or $\ge 50\%$ decrease in platelet count, or absolute neutrophil count will NOT exclude a patient from continuing the study. Work-up of such decreases to exclude auto-immune hemolytic anemia, pure red cell aplasia, or idiopathic thrombocytopenic purpura (ITP) should be considered.
- 11.236 For patients who achieve a CR or nodular PR, progression will be defined as recurrence of circulating leukemia cell clone and an ALC
 >5000 or recurrence of adenopathy >1.5 cm not due to a tumor flare.
- 11.24 STABLE DISEASE (SD): Patients who do not meet criteria for CR, CRi, nPR, CCR, PR, or PD will be classified as having "stable disease". The first formal response evaluation should occur no sooner than the end of cycle 2.
- 11.25 Not PD: The patient was evaluated for progression only this cycle and a formal response evaluation did not occur. The patient did not meet the criteria for progression per section 11.23.

Note: Formal response evaluation should occur every 2 cycles during treatment, with the first response evaluation occurring at the end of cycle 2. Formal response evaluation should occur every cycle during observation. Objective status should be classified as PD vs. Not PD on cycles when a formal response evaluation does not occur.

11.3 EVALUATION OF MINIMAL RESIDUAL DISEASE (MRD): MRD will be assessed by flow cytometry and/or PCR for patients who achieve a CR/nPR/CRi. 43 MCCC Addendum 1

| | CCR ¹ | CR ² | CRi ³ | nPR ⁴ | PR ⁵ | PD ⁶ |
|---------------------------|--------------------------------------|--------------------------------------|------------------------------------|-------------------------------------|--|--|
| PHYSICAL EXAM | | | | | I | |
| Nodes ⁷ | None | None | None | None | ≥50% ↓ | \geq 50% \uparrow , new nodes |
| Liver/spleen ⁸ | Not palpable | Not palpable | Not palpable | Not palpable | ≥50% ↓ | \geq 50% \uparrow , newly palpable |
| Symptoms | None | None | None | None | N/A | Ñ/Â |
| PERIPHERAL BLOC | DD | | | · | | |
| ANC | >1500/µL | >1500/µL | See footnote 3 | >1500/µL | >1500/µL or >50% improvement from baseline | See footnote 6 |
| Platelets | >100,000/ µL | >100,000/µL | See footnote 3 | >100,000/µL | >100,00/µL or >50% improvement from baseline | See footnote 6 |
| Hemoglobin | >11.0 g/dL without transfusion | >11.0 g/dL without transfusion | See footnote 3 | >11.0 g/dL without transfusion | >11.0 g/dL or >50% improvement from baseline without transfusion | See footnote 6 |
| Lymphocytes | <4000/µL | <4000/µL | <4000/µL | <4000/µL | \geq 50% \checkmark | $\geq 50\% \uparrow$ to at least $5,000/\mu$ L |
| BONE MARROW | N/A | <30% lymphocytes; no nodules | <30% lymphocytes; no nodules | bone marrow nodules ⁴ | N/A | N/A |

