3.0 Patient Eligibility

Phase I only: Prior to discussing protocol entry with the patient, call the MCCC Registration Office () for dose level and to insure that a place on the protocol is open to the patient.

- 3.1 Inclusion Criteria
 - 3.11 Understand and voluntarily sign an informed consent form.
 - 3.12 Age \geq 18 years.
 - 3.13 Able to adhere to the study visit schedule and other protocol requirements.
 - 3.14 Diagnosis of B-CLL, confirmed by flow cytometric analysis and as per the criteria outlined by the IWCLL/Hallek December 2008. (Refer to Appendix III).
 - 3.15 Any prior therapy for B-CLL must have been discontinued \geq 28 days prior to registration.
 - 3.16 Patients must have an absolute lymphocyte count (ALC) of more than 5,000 cell/mm³.
 - 3.17 During Phase I: All patients with relapsed disease will be eligible if they have received at least 1 prior standard CLL therapy^{*} and no more than 4 prior therapies (one of which must be a purine analog and/or an alkylating agent).

During Phase II: All patients with relapsed disease will be eligible if they have received a minimum of 1 prior standard therapy^{*} and a maximum of 2 prior treatments (one of which must be a purine analog and/or an alkylating agent) for B-CLL and have developed relapse disease.

Note: Patients who have refractory disease (defined as – progressive disease on last treatment, or less than 6 months of clinical response to the last treatment) will not be eligible.

* Standard Therapies are defined as those listed in the NCCN guidelines for treatment of CLL.

- 3.18 ECOG performance status of 0, 1 or 2 at registration (see Appendix I).
- 3.19a The following laboratory values obtained \leq 14 days prior to registration:
 - Absolute neutrophil count $\geq 1500/\text{mm}^3$
 - Platelet count \geq 30,000/mm³
 - Serum creatinine $\leq 1.5 \text{ x ULN}$.
 - Total bilirubin $\leq 1.5 \text{ mg/dL}$ or direct bilirubin $\leq 1.0 \text{ mg/dL}$ for patients with Gilbert's syndrome
 - SGOT (AST) and SGPT (ALT) ≤ 2 x ULN or ≤ 5 x ULN if hepatic disease is present.

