8.2 Lenalidomide

A new course of treatment may begin on the scheduled Day 1 of a new cycle if:

- The ANC is $\geq 1,000/\mu$ L;
- The platelet count is $\geq 25,000/\mu$ L;
- Any lenalidomide-related allergic reaction/hypersensitivity or sinus bradycardia/ other cardiac arrhythmia adverse event that may have occurred has resolved to ≤ grade 1 severity;
- Any other lenalidomide-related adverse event that may have occurred has resolved to \leq grade 2 severity.

If these conditions are not met on Day 1 of a new cycle, the subject will be evaluated weekly and a new cycle of lenalidomide will not be initiated until the toxicity has resolved as described above. If lenalidomide dosing was omitted during the previous cycle and was restarted with a one-level dose reduction without requiring an interruption for the remainder of the cycle, then that reduced dose level will be initiated on Day 1 of the new cycle. If lenalidomide dosing was omitted for the remainder of the previous cycle or if the new cycle is delayed due to toxicity newly encountered on the scheduled Day 1, then the new cycle will be started with a one-level dose reduction.

If either drug is discontinued, patient will come off treatment and go to event monitoring.

| → → Use the NCI Common Terminology Criteria for Adverse Events (CTCAE) version 4.0 unless otherwise specified $\leftarrow \leftarrow$ | | | | |
|---|---|--------------|---|--|
| CTCAE System/Organ/Class (SOC) | ADVERSE EVENT | AGENT | ACTION | |
| | BASED ON INTERVAL | ADVERSE E | EVENTS (Days 2-28) | |
| Investigations | Platelet count decreased*: (Platelets < 10,000/mm ³) | | Omit dose. Follow CBC weekly. If thrombocytopenia resolves to ≤ grade 3 restart lenalidomide at the same dose level. | |
| | | | If thrombocytopenia < 10,000/mm³ recurs, reduce dose by one dose level (5 mg) and continue therapy when platelet count ≥ 25,000/mm³. | |
| | Grade 4 Neutrophil count | | • Omit dose. | |
| | decreased* | | • Follow CBC weekly. | |
| | | Lenalidomide | If neutropenia has resolved to ≤ grade 2, resume dose at same level with GCSF support. | |
| Blood and lymphatic | ≥ Grade 3 Febrile | omi | Omit dose. | |
| system disorders | neutropenia | de | • Follow CBC weekly. | |
| | | | If neutropenia has resolved to ≤ grade 2, resume dose at same level with GCSF support. | |

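### The partial-response blood-count requirement does not exclude a neutrophil count held up by G-CSF or a transfused platelet count, so drug-related cytopenia need not bar a PR when counts are supported

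*Combined protocol and SAP*

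**What the plan says.** **Structure of PR (protocol 11.22).** The patient must show "at least two of the features in Sections 11.221, 11.222, and 11.223 below (if abnormal prior to therapy"): a fall of at least 50% in lymphocytes, nodes, or liver and/or spleen. One or more of three blood-count lines must also be met, and the whole must hold for at least 2 months.

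**The three count lines.**
- 11.224: "Neutrophils >1500/ul or 50% improvement over baseline". No mention of growth factors.
- 11.225: "Platelets >100,000/ul or 50% increase over baseline". No mention of transfusion.
- 11.226: hemoglobin above 11.0 g/dL or a 50% rise, with transfused values excluded.

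**CR lines (11.214).** The platelet line reads "Platelets >100,000/ul (untransfused"), and hemoglobin carries the same exclusion. The neutrophil line (above 1500) has no growth-factor exclusion.

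**Summary table (with 11.4).** Transfused hemoglobin is excluded in the CR and PR columns. The platelet cells carry no such exclusion in either column, which for CR contradicts 11.214.

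**Entry (3.19a).** ANC at least 1500/mm³ and platelets at least 30,000/mm³.

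**Support on study.** After grade 4 or febrile neutropenia, the 8.2 table says "If neutropenia has resolved to ≤ grade 2, resume dose at same level with GCSF support". Section 9.2 allows growth factors and blood products as clinically warranted and in line with guidelines. The only ban is on growth factors in cycle 2 of phase I.

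**Endpoint (16.411).** CR, CRi, CCR, nPR and PR all count as success.

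**The concern.** A count requirement in a response definition should show that the marrow has kept or recovered its function. Here the neutrophil line asks for nothing beyond what entry already guarantees, and it alone is enough. It can fail only through on-study neutropenia, which is where supportive care acts. If a supported value satisfies the line, the requirement partly measures the use of G-CSF.

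The plan treats supported values as uninformative elsewhere: it excludes transfused CR platelets, CR hemoglobin and PR hemoglobin. The silence on G-CSF and on PR platelets therefore looks like an omission. The mismatch between 11.214 and the summary table means that two assessors could apply different rules to the same patient.

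At stake is the primary count. The final decision turns on 14 versus 15 successes among 37 patients, and one patient is 1/37 = 2.7 percentage points.

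**Working it through.** **1. Who is affected.** Following the text literally, a patient is scored PR only because of support by the G-CSF route when all of these hold:
- at least two of 11.221 to 11.223 are met, for 2 months;
- platelets are at or below 100,000 without a 50% rise;
- hemoglobin is at or below 11 without a 50% rise;
- ANC is above 1500 on G-CSF and would not be without it.

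The last condition can arise under the plan. Section 8.2 lets a new cycle start at an ANC of 1,000, and lets dosing resume with G-CSF once neutropenia is grade 2 or better, which in Appendix V starts at 1,000. Both are below the 1500 response cut-off. In phase II, nothing stops growth-factor use before the first formal evaluation at the end of cycle 2. The phase I ban in cycle 2 covers only the 6 MTD patients carried forward.

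**2. The plan's own operating characteristics (16.31 and 16.32).** Stop if there are 4 or fewer successes in 14; positive if there are 15 or more in 37. With X1 ~ Bin(14, p) and X2 ~ Bin(23, p):

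P(positive) = Σ (x = 5 to 14) P(X1 = x) · P(X2 ≥ 15 − x)

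| True rate p | 0.30 | 0.35 | 0.40 | 0.45 | 0.50 |
|---|---|---|---|---|---|
| Recomputed P(positive) | 0.0954 | 0.2525 | 0.4744 | 0.6937 | 0.8526 |
| Stated in 16.32 | 0.10 | 0.25 | 0.47 | 0.69 | 0.85 |

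The stated table is reproduced.

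**3. Effect on the false-positive rate.** The documents give no share, so x is an assumption: the fraction of patients who would be non-responders if supported counts were excluded, but who are scored PR through a supported count. With a true rate of 0.30, the observed rate is p = 0.30 + 0.70x.

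| Assumed x | Observed p | Expected extra successes in 37 (37 × 0.70x) | P(positive) |
|---|---|---|---|
| 0 | 0.3000 | 0 | 0.095 |
| 0.5% | 0.3035 | 0.13 | 0.10 (0.1035) |
| 2% | 0.3140 | 0.52 | 0.13 |
| 3% | 0.3210 | 0.78 | 0.15 |
| 5% | 0.3350 | 1.30 | 0.20 |

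**4. Effect of stricter wording on power.** Suppose the 50% target was set with the present wording in mind, and the exclusions remove 5% of responders. The rate becomes 0.50 × 0.95 = 0.475, and P(positive) falls from 0.853 to 0.783.

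**The case against.** The strongest reply is that these patients are not plain non-responders. Each has at least two disease reductions of 50% or more, sustained for 2 months, and the count lines cannot create a response alone. That stands, and it limits the point to a weak component of PR.

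Several stronger readings are tempting, but the documents do not support them:
- *Marrow failure never bars a response.* Failure of all three lines without support still fails 11.22. For otherwise complete responders, the plan deliberately counts drug-related cytopenia as success, through CRi.
- *CR is inflated in the primary analysis.* CR and CRi are both successes in 16.411, so moving a patient between them leaves the primary count unchanged. Section 16.431 compares CR with PR, does not name CRi, and is exploratory.
- *Transfusion is as likely a route as G-CSF.* Keeping platelets above 100,000 by transfusion for 2 months is implausible. The missing word in 11.225 is mainly an inconsistency.
- *The problem concentrates in Rai III/IV patients.* Appendix II defines those stages by anemia and thrombocytopenia, and every entrant meets the ANC threshold. Nothing ties G-CSF use to those stages.

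Two further replies keep some force. Section 11.2 adopts an external criteria paper (reference 59), which may carry its own qualifier; it is not available here, and the explicit lines of section 11 do not repeat one. If the 30% benchmark was scored equally leniently, part of any bias cancels; the documents do not say.

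**Conclusion.** The point holds as a gap in the endpoint definition. Read literally, 11.22 lets a G-CSF-dependent ANC complete a PR in a patient with real disease reduction but inadequate platelets and hemoglobin. The summary table also contradicts 11.214 on CR platelets, which needs reconciling whatever the size of the bias.

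The effect on the primary result is probably small and cannot be estimated from the documents. At an assumed 0.5% the false-positive rate stays at about the stated 0.10; it reaches 0.20 only at an assumed 5%. These figures assume a true rate of 30% with supported counts excluded, and a benchmark not scored with the same leniency. The change is worth making because it is cheap and brings these lines into step with the plan's own handling of supported values.

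**What to change.** 1. Add *without growth-factor support* to the neutrophil lines of 11.214 and 11.224, and *untransfused* to 11.225.
2. Make the 11.4 summary table match, including the CR platelet cell.
3. State that a patient who meets CR except for a supported ANC is classified as CRi. This affects only the description of response quality.
4. Record growth-factor and transfusion dates on the evaluation form. Section 9.3 already puts blood products in the medical record, and Appendix V asks for growth-factor use to be documented, but no form listed in 18.1 is dedicated to either.
5. Report how many PRs depend on a supported count. If the present definition is kept, give this as a sensitivity analysis of the response rate.

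The cost is protocol wording and one form field, with no extra visits or tests. The response rate may be slightly lower. So may power, if the 50% target assumed the present wording: the loss of 5% of responders worked above takes it from 0.85 to 0.78.
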